Assessment Methodology. Participants will complete the assessment battery at weeks 0, 4, 8 and 21, consisting of self-report questionnaires and performance-based tests of cognition and functioning. Performance-based tests will not be administered at week 4, however, to avoid practice effects. Collateral informants (e.g., spouse, adult child, relative), when available, will complete questionnaires at weeks 0, 4, 8, and 21. Study measures and the rationale for including them are listed in **Table 5**. Measures will take < 3.5 hours to complete at week 0 (baseline), < 1 hour at week 5, and approximately 3 hours at weeks 8 and 21 (follow up). We have selected measures based on 4 criteria: 1) importance for assessing constructs evaluated in our aims, 2) brevity (to reduce subject burden), 3) reliability, and 4) demonstrated validity. The rationale for including each study measure is listed in **Table 5** and further described below. Data collected at the second site, VAPORHCS, will be transferred to VASDHS via drive behind the VA firewall, as we have done in a previous study. Fitbit data will be collected at the VASDHS site only.

Fitbit Charge 2 (<https://www.fitbit.com/charge2>): This non-invasive, water resistant device, which is worn around the wrist, will be used to measure participants' activity levels, heart rate, and sleep quality. The Fitbit uses a three-dimensional accelerometer to sense movement. It measures steps taken, distance walked, calories burned, active/inactive minutes, stationary time, heart rate, hours and quality of sleep, as well as stages of sleep. The Fitbit's measurement of self-paced and prescribed intensity exercise has been validated against the Omron HJ-720IT accelerometer and direct observation.

Table 5. Study Measures

Measure	Purpose /Specific Aim: Hypothesis	Construct Assessed	Weeks Administered	Time (min)
Patient Health Questionnaire-9 (PHQ-9) [74].	Subject characterization; Exploratory Aim 4.	Depression symptom severity.	0	2
General Anxiety Disorder-7 Scale (GAD-7) [75].	Subject characterization; Exploratory Aim 4.	Anxiety symptom severity.	0	2
PTSD Checklist (PCL)	Subject characterization; Exploratory Aim 4.	PTSD symptom severity.	0	2
Wide Range Achievement Test-4-Reading (WRAT-4) [76].	Subject characterization; Exploratory Aim 4.	Reading ability (premorbid IQ estimate).	0	5

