Data analyses will proceed in stages: 1) First, descriptive statistics and exploratory analyses will be used to assess the normality of the data and homogeneity of variance. The continuous outcome data will be transformed if necessary by using an appropriate transformation such as the log transform for skewed long tailed data. Similarly, potential covariates will be summarized with descriptive statistics and graphs to determine the most appropriate way to treat these variables. In addition, the results will be inspected for bias due to dropouts or missing data. 2) Although we don't anticipate any baseline differences, we will compare any differences among groups and sites on baseline measures. Any statistically and clinically significant differences will be controlled for in subsequent analyses by adding the target variables as covariates to the model. 3) We propose to use mixed effects modeling to account for clustering structure of the data (i.e., repeated assessments within an individual, groups, therapists and sites) for main hypotheses testing. The mixed effects approach is more powerful than traditional methods and allows the inclusion of subjects with missing data or those who were terminated early in the study, without relying on data imputation procedures. Two specific forms of the mixed effects models of random regression models (RRM), also known as hierarchical linear models (HLM) or multilevel models, and mixed model analysis of variance (MMANOVA) will be considered. Each outcome variable will be graphed versus time for each subject to evaluate what function of time best describes the data. If the change is linear we will proceed with the HLM structure. If the time pattern is not immediately apparent we will proceed with the MANOVA. 4) We will use the extension of the Pattern-Mixture models [89] which allow subject-to-subject heterogeneity, to assess if there is bias due to drop out or missing data. Furthermore, the randomness of missing data will be examined according to recommended procedures [90], which includes comparing group differences in the primary outcomes of subjects with versus without missing data. Specific plans for testing each hypothesis are below.

H1: Compared to those in SC, participants in ME-CCT will show significant improvements in objective cognitive performance and functional capacity.

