Dependent variables: Neurocognitive composite score (Average z score across subtests in the Neurocognitive Battery detailed in **Table 6**); Functional capacity composite score (Average z score across subtests in the Functional Capacity Battery detailed in **Table 7**). **Independent variables:** Treatment group (2 levels, ME-CCT and SC), and Time (4 levels, Weeks 0, 4, 8, 21). **Statistical Analysis:** We will analyze data on all randomized subjects for whom we have a baseline assessment and at least one post-baseline evaluation. Data will be analyzed by mixed effects model methods [91-93] for linear or non-linear trends based on earlier inspection of data. The mixed effects model method provides an estimate of the individual variability around the population trend, the variability of the individual intercepts (baseline values) and slopes (changes across time), and the correlation between them. A fully saturated treatment X time model will be utilized for inference. Covariance structure will be chosen based on Akaike's Information Criterion (AIC). Random group level treatment effects will also be evaluated for importance based on the model AIC. Denominator degrees of freedom will be calculated using the Kenward-Roger small sample correction. The effects of site, therapist and their interaction with treatment will be included and tested. However, we do not anticipate any significant interactions or main effects of these factors given our balanced study design (equal numbers at each site in each group), our standard training and operating procedures at both sites and with all therapists, and our previous analyses from our similarly-designed study (our CCT for TBI study). In any case, the analysis procedures will include these factors and their interaction effects to avoid allowing site or therapist effects to bias treatment comparisons. If we detect any imbalances between the treatment groups, we will follow the primary analyses above with subsequent analyses considering the imbalances to verify that the conclusions are not affected by the imbalances. Analyses will be conducted within and across nested levels of the study design; this will involve within-subject analyses (comparison of occasions of measurement nested within an individual), as well as between-subject analyses. In addition, any treatment group comparison will be adjusted for subject-specific characteristics, and adjustments for changes in these characteristics over the course of the study can be incorporated into the single-subject analyses. **Power Analysis:** In addition to the procedures described by Hedeker and colleagues [94] for Random Regression Models (the RMASS program provided by Hedeker), we used several standard other methods for power calculation and estimation of needed sample size. We selected the sample size that would provide us with a minimum of 80% power across all hypotheses and their expected effect sizes. We used this method with the following assumptions to estimate required sample size: the mixed design of two groups (ME-CCT and SC) and time (4 levels, weeks 0, 4, 8, 21) where the slope is the dependent measure; alpha-level of .02, nature of the hypothesis (two-sided), dropout rate (up to 20%), autoregressive covariance structure (with correlation between sequential assessments set at .45) of the longitudinal data, medium effect size as a between-group difference increasing linearly from 0 at baseline to .5 SD units at the last time point, various correlations (.2, .5, and .8) between the repeated measures, and various effect sizes from medium to large. We estimated that with a final sample size of 180 participants (216, with a drop-out rate of 20%), the study will have

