
minimum 85% power to yield a statistically significant result for a medium effect size. As is noted in the previous sections, we have found medium to large post-treatment effect sizes for several outcome measures in our previous studies.

H2: Compared to those in SC, participants in ME-CCT will show significant improvements on measures of subjective cognitive complaints, subjective functioning, and collateral measures of everyday functioning.

Dependent variables: Subjective Everyday Functioning Composite Score (average total score across the two Neuro-QOL scales, namely the Applied Cognition Executive Function Scale, and the Applied Cognition General Concern Scale); ECog.

Independent variables: Treatment group (2 levels, ME-CCT and SC), and Time (4 levels, Weeks 0, 4, 8, 21). Statistical Analyses: Data will be analyzed similar to the method described for H1. Power Analyses: Power analyses were conducted similarly to H1, and the study will have 87% power to yield a statistically significant result for a medium effect size for H2. We have found large effects on subjective cognitive/functional complaints in previous studies.

H3: Compared to those in SC, participants in ME-CCT will show increased participation in protective activities, as measured by physical and cognitive activity inventories.

Dependent variables: Cognitive Activity Inventory, CHAMPS Physical Activity Inventory for Older Adults. Independent variables: Treatment group (2 levels, ME-CCT and SC), and Time (4 levels, Weeks 0, 4, 8, 21). Statistical Analyses: Data

will be analyzed similar to the method described for H1. Power Analyses: Power analyses were conducted similarly to H1, except the alpha level was set at .01; the study will have 80% power to yield a statistically significant result for a medium effect size for each dependent measure evaluated through H3.

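### H1's stated 85% power is for a slope over four visits; the inference model is saturated over visits, names no deciding contrast or baseline handling, and has only three measured visits

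*Combined protocol and SAP*

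**What the plan says.** All of this is in Section 9 of the combined protocol and SAP.

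- **Power (H1, Power Analysis).** The design is "time (4 levels, weeks 0, 4, 8, 21) where the slope is the dependent measure". The effect is a "between-group difference increasing linearly from 0 at baseline to .5 SD units at the last time point", with two-sided alpha .02 and autoregressive correlation .45. Correlations of .2, .5 and .8 are also listed. With 180 analysed, the plan reports "minimum 85% power to yield a statistically significant result for a medium effect size".
- **Inference (H1, Statistical Analysis).** "A fully saturated treatment X time model will be utilized for inference". The same paragraph says that the models will be fitted "for linear or non-linear trends based on earlier inspection of data".
- **Model form (general analysis plan, stage 3).** After each outcome is graphed against time: "If the change is linear we will proceed with the HLM structure". Otherwise: "If the time pattern is not immediately apparent we will proceed with the MANOVA".
- **Schedule (Assessment Methodology).** "Performance-based tests will not be administered at week 4, however, to avoid practice effects". Table 5 accordingly lists both co-primary composites at weeks 0, 8 and 21, while the H1 independent variables give Time four levels.

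Nowhere does the plan say whether H1 is decided by a slope difference, a week-8 or week-21 difference, a change from baseline, or a joint test. Nor does it say whether the arms share a baseline mean.

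**The concern.** A model saturated in visit has no single slope, so the quantity that was powered is not a parameter of the model named for inference. Several tests can be drawn from that model, and their power differs widely under the plan's own assumptions. If the test used is a weaker one, a null H1 result would be read against 85% power that the test did not have. If the choice waits until outcomes have been plotted, the deciding test for both co-primaries is settled from the data.

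**Working it through.** **Inputs.** From the H1 power text: two-sided alpha .02 (critical z 2.326), 180 analysed (90 per arm), difference reaching .5 SD at week 21, AR(.45). From Table 5: visits 0, 8, 21. I use unit SD and normal or chi-square approximations, and ignore clustering. The plan leaves two things open, so ranges cover both: growth linear in weeks or in visit order, and week 4 either kept as a gap in the AR structure (lags 0, 2, 3) or removed (lags 0, 1, 2).

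**1. The plan's own figure.** For visit times x scaled to 1 at week 21 and V = (2/90) × the correlation matrix, a slope test with equal baselines has z = .5 × √(x′V⁻¹x). With four visits linear in weeks, z = 3.380 and power is Φ(3.380 − 2.326) = 85.4%; in visit order it is 88.0%. The stated minimum of 85% therefore reproduces. If a free baseline difference is added to the same four-visit slope, power is 57–63%.

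**2. The three measured visits, 90 per arm, AR(.45).**

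| Test | Baselines taken as equal | Arm-specific baselines |
|---|---|---|
| Slope | 85.3–90.4% | 56.5–66.0% |
| Week 21 | 85.1–86.4% (difference) | 56.4–62.9% (change) |
| Joint interaction, 2 df | 77.1–84.0% | 45.5–55.0% |

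A plain week-21 comparison that ignores baseline has 84.8%.

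Hand checks:
- Plain week 21: .5/√(2/90) = .5 × √45 = 3.354, giving 84.8%.
- Week 21, equal baselines, lag 3: .5/√[(2/90)(1 − .45⁶)] = 3.368, giving 85.1%.
- Week-21 change, lag 3: .5/√[(2/90) × 2(1 − .45³)] = 2.488, giving 56.4%.
- Joint test, free baselines: noncentrality 6.20 to 7.50 against a critical value of 7.82, giving 45.5–55.0%.

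**3. Where the loss comes from.** Freeing the baselines costs the slope 22 to 31 points (86.4 to 64.5; 87.6 to 56.5). Moving from slope to joint test with baseline handling held fixed costs 6 to 11 points (90.4 to 84.0 with equal baselines; 62.8 to 51.8 with free baselines). Dropping week 4 costs almost nothing: the equal-baseline slope, linear in weeks, goes from 85.4% to 85.3%.

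**4. The other listed correlations**, taken as exchangeable, three visits, 90 per arm:

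| Test | .2 | .5 | .8 |
|---|---|---|---|
| Slope, free baselines | 63–65% | 85–86% | 99.9% |
| Joint, free baselines | 52–54% | 77–78% | 99.6% |
| Week 21, equal baselines | 86.4% | 93.9% | 99.9% |

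**5. Choosing the form by plot.** In 1,000,000 simulated trials under AR(.45), the free-baseline slope and the joint test reach different verdicts in about 14% (slope alone significant about 12.5%, joint alone about 1.5%). The figure is about 10% at correlation .5 and 0.3% at .8. Under the null, one or the other rejects in 3.1%, against 2% nominal. That is a ceiling, since it counts either result; selection by plot shape would give less.

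**6. Sample size.** 216 × .8 = 172.8, or 86.4 per arm, not 90. At that size the week-21 difference with equal baselines has 83.5–84.8%, the free-baseline slope 55–64%, and the joint test 44–53% (free) or 75–82% (equal). Dropouts who have a week-8 visit add a little information, so these figures are slightly low.

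**The case against.** The stated power can be defended. The equal-baseline slope at 90 per arm stays at or above 85% under AR(.45) and under exchangeable .2, .5 and .8. At correlation .5 even the free-baseline slope reaches 85–86%. A saturated model can supply any 1-df contrast, including a week-21 difference with about 85% power. The plot rule sits in the general plan, where two forms are only to be considered; the later H1 text says which model will be used, and the graphs are drawn per subject, not by arm. All of this stands. It shows that 85% is attainable, not that the plan has committed to a test that attains it. The general plan makes baseline variables covariates only if the arms are found to differ, and the H1 text speaks of adjusting for subject characteristics. Neither commits to a shared baseline mean or to adjustment for the baseline score.

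A reader might go further and infer that the saturated model cuts power from 85% to 46–55%. The documents do not support that. They never name a joint interaction test, and the comparison also changes the baseline handling, which accounts for most of the fall. A reader might also infer that the plot-based choice seriously inflates the error rate; the ceiling is about 1 percentage point.

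**Conclusion.** The point holds as a gap in specification with a real consequence for power. The stated 85% belongs to one estimator on a four-visit schedule; the inference model is another, on three measured visits, with contrast and baseline handling left open. Under AR(.45) at 90 per arm, the admissible 1-df tests run from 56% to 90%, and baseline handling is the main driver. The shortfall is similar at correlation .2, smaller at .5 and gone at .8. The four-level wording of Time is an error for H1 but costs almost no power, and the plot rule adds at most about 1 point to the 2% error. These figures assume complete data at the stated size, the plan's linear growth to .5 SD, and no clustering. This should be corrected before outcomes are inspected, but it does not show the trial to be underpowered for every reasonable H1 test.

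**What to change.** For H1, set Time to weeks 0, 8 and 21. Before any outcome is inspected, name one 1-df contrast per co-primary, state its visit, and either constrain baseline means to be equal or adjust for the baseline score. This replaces the plot-based choice. The visit is the sponsor's decision; week 21 is the one that matches the stated power assumption. Report the other visit and any joint test as supportive.

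Restate power for that contrast on three visits at 172.8 participants, and keep the word minimum only if it holds across the listed correlations. For the constrained week-21 difference under AR(.45), expect 83.5–84.8% before clustering. Participants are randomized in therapy groups of at least 6, so an allowance is needed, but the documents give no ICC. As an illustration only, groups of 6 inflate the variance by 1 + 5 × ICC: an assumed ICC of .02 gives about 79–81%, and .05 gives about 73–75%.

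The cost is wording and a recalculation, with no new data or visits. The sponsor must commit to one time point and accept a stated power that will probably fall slightly below 85%, or further once clustering is allowed for.

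### The stated 85%, 87% and 80% slope power does not follow from the stated inputs when the arms may differ at baseline; it needs an assumption that the plan does not state

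*Combined protocol and SAP*

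**What the plan says.** All of this is in Section 9, under the hypothesis-specific analysis plan and power analyses.

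- **Design and test.** The H1 power paragraph takes two arms, four visits (weeks 0, 4, 8, 21), the slope as the quantity tested, two-sided alpha .02, up to 20% dropout and a final sample of 180 from 216 recruited.
- **Covariance.** It assumes an "autoregressive covariance structure (with correlation between sequential assessments set at .45) of the longitudinal data". The same sentence also lists "various correlations (.2, .5, and .8) between the repeated measures".
- **Effect.** It assumes a "medium effect size as a between-group difference increasing linearly from 0 at baseline to .5 SD units at the last time point".
- **Results.** H1 has "minimum 85% power to yield a statistically significant result for a medium effect size". H2, computed similarly, has "87% power to yield a statistically significant result for a medium effect size for H2". H3 was handled the same way "except the alpha level was set at .01; the study will have 80% power".
- **Inference model.** The H1 statistical analysis paragraph says that a saturated treatment-by-time model is used for inference. It also describes person-level intercepts and slopes. No sentence constrains the two arms to one baseline mean.
- **Visits.** Assessment Methodology says that the performance-based tests, which make up both H1 outcomes, are not given at week 4. H1 therefore has three measured visits (0, 8, 21).

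**The concern.** Under an autoregressive structure the correlation decays with distance. At .45 per step, week 0 and week 21 correlate at only .45³ = .09. A person's change from baseline is then very noisy, and a slope test that estimates a baseline mean for each arm must carry that noise. Power of 85% for a .5 SD difference with 90 per arm looks too high for such a test.

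The plan says that the sample size was chosen to give at least 80% power for every hypothesis. If the test actually fitted has nearer 55-65%, a null result would be read as a well-powered negative when it is not.

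**Working it through.** **Inputs.** SD 1; difference at visit time t equal to .5·t/t_last; n = 90 per arm (180/2); AR(1) with .45 between successive visits; z(.99) = 2.326 for alpha .02 and z(.995) = 2.576 for alpha .01. Like the plan's listed inputs, the check makes no allowance for treatment-group clustering.

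**1. Free baseline, by hand (four equally spaced visits, least-squares slopes).** Contrast c = (-3, -1, 1, 3); mean difference μ = (0, .167, .333, .5); c′μ = 1.667.

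c′Σc = 20 + 2(.45×5 - .2025×6 - .0911×9) = 20.43

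z = 1.667 / √(2×20.43/90) = 2.474

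Power = Φ(2.474 - 2.326) = **55.9%** at .02, and Φ(2.474 - 2.576) = **45.9%** at .01.

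**2. Free baseline, generalised least squares.** The variance of the slope difference is the matching diagonal element of (Σ_arm n·X′V⁻¹X)⁻¹, with an intercept and a slope for each arm. SE is on the scale of the last-visit difference.

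| Visits | SE | z = .5/SE | Power at .02 | Power at .01 |
|---|---|---|---|---|
| Four, equal spacing | .2003 | 2.50 | 56.8% | 46.8% |
| Weeks 0, 4, 8, 21 | .1876 | 2.67 | 63.3% | 53.6% |
| Weeks 0, 8, 21 (H1) | .1853 | 2.70 | 64.5% | not applicable |

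If dropout accrues evenly from 108 to 86.4 per arm (20%), the .02 column becomes 60.2%, 64.4% and 66.4%, and the four-visit .01 values become 50.4% and 54.7%. With all 216 retained, power at .02 is 65.9%, 72.3% and 73.5%, so the dropout assumption cannot close the gap. Simulation of 20,000 trials (t test on per-person slopes, n = 90) gave 56.1%, 62.4% and 63.4% at .02. If the correlation decays by elapsed weeks instead of by visit, four-visit power is a little lower: 53.5% at .02 and 43.6% at .01.

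The saturated model has no single slope, so its week 0 to 21 change contrast was checked as well. SE = √(2×2(1 - .0911)/90) = .201, giving 56.4% at .02 and 46.5% at .01.

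**3. What does come close to 85/87/80 (90 per arm).**

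| Calculation | Power at .02 | Power at .01 | What it adds or changes |
|---|---|---|---|
| AR(.45), common baseline mean, four visits | 85.4% (weeks) to 88.0% (equal) | 78.9% to 82.2% | Unstated baseline constraint |
| Constant .45, free baseline, four visits | 85.2% (equal) to 85.8% (weeks) | 78.7% to 79.4% | Different covariance |
| AR(.8), free baseline, equal spacing | 85.7% | 79.4% | Correlation other than .45 |
| Last visit only, .5 SD | 84.8% | 78.2% | Not a slope test |

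Constant .45 by hand: c′Σc = 20(1 - .45) = 11; z = 1.667/√(2×11/90) = 3.371; Φ(3.371 - 2.326) = 85.2%. Last visit by hand: z = .5/√(2/90) = 3.354; Φ(3.354 - 2.326) = 84.8%. With a common baseline and H1's own three visits, AR(.45) gives 86.4% at .02.

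**4. The word "minimum" (alpha .02, four visits, 90 per arm).** At correlation .2 with a free baseline, power is 54-57% (AR) or 68-69% (constant). With a common baseline, AR and actual weeks, it is 86.6% (.2), 85.4% (.45), 86.0% (.5) and 97.1% (.8), never below 85%.

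**5. Detectable difference for 85% power, free baseline.** (2.326 + 1.036)×SE runs from 3.363×.1853 = .62 SD (three visits) to .5×3.363/2.474 = .68 SD (step 1).

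**The case against.** The strongest reply is that the power paragraph never says whether the power model estimated a baseline difference. Its effect starts at 0 at baseline, and a common-baseline slope test with every printed numerical input kept gives 85.4-88.0% and 78.9-82.2%, which brackets all three figures. That reading also makes "minimum" true at each listed correlation. Moreover, a saturated model has no single slope parameter, so it is not literally the model that was powered.

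Much of this stands. The shortfall depends on a free baseline, and the printed figures may have been correct for the calculation behind them. Two stronger readings that a reader might draw are therefore not supported. One is that .45 must have been entered as a constant correlation: three other routes come about as close, and the text mentions several power methods without tying any to a printed figure. The other is that 216 participants cannot give the stated power under the plan's covariance: with a common baseline they approximately can.

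The reply does not rescue the plan as written. The only inference model described leaves the arms free at week 0, and both its slope version and its week 0 to 21 contrast fall far short.

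**Conclusion.** The concern holds in conditional form. For a slope test with a free baseline, which is what the stated inference model implies, AR(.45) at N = 180 gives about 56-66% for H1 and H2 against 85% and 87%, and 46-55% for H3 against 80%. The shortfall is roughly 19 to 34 points, and no hypothesis reaches the plan's 80% floor. "Minimum 85%" likewise fails at correlation .2 only when the baseline is free.

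The result rests on unit SD at every visit, the stated linear effect, correlation decaying by visit order and no clustering. It does not establish which calculation the sponsor ran. Nor does the text explain why H1 and H2, computed similarly at what appears to be the same alpha, differ by two points.

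**What to change.** **Preferred.** Prespecify that H1 to H3 are tested with week 0 kept as a response and one baseline mean for both arms. Randomisation justifies the constraint. Under AR(.45) with 90 per arm, power is about 85-88% at .02 and 79-82% at .01, so the H1 and H3 figures stand approximately. H2's 87% should be re-run, because it lies between the actual-weeks value (85.4%) and the equal-spacing value (88.0%).

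**Otherwise.** Keep the free-baseline model and restate power as about 56-66% (H1, H2) and 46-55% (H3), or state a detectable difference of about .62-.68 SD for 85% power at alpha .02. Remove "minimum" in that case.

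**Either way.** State the covariance, correlation, visit spacing and baseline handling behind each printed figure. Compute H1 on weeks 0, 8 and 21. Make the powered test and the fitted model the same.

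**Cost.** Protocol wording and a re-run of the power calculation, settled before any unblinded analysis. Enrolment stays at 216, with no added visits. The only downside is a less favourable printed power if the free-baseline model is kept.

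### The single 87% power for H2 makes no allowance for retained participants without an informant, so it cannot be taken as the power for the ECog

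*Combined protocol and SAP*

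**What the plan says.** Under H2 in the hypothesis-specific analysis plan (Section 9), the dependent variables are the Neuro-QOL composite and the ECog. The power text is brief. It refers its method back to H1, and the result it reports is that "the study will have 87% power to yield a statistically significant result for a medium effect size for H2". No sample size or alpha is given for H2 itself. H3, by contrast, states its own alpha where it departs from H1.

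The H1 power paragraph uses two-sided alpha .02, drop-out of up to 20% and a final sample of 180 from 216 recruited. It defines the effect as a "medium effect size as a between-group difference increasing linearly from 0 at baseline to .5 SD units at the last time point". It also says that the sample size was chosen to give at least 80% power for every hypothesis at its expected effect size.

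The Retention and reimbursement paragraph bases the 20% on participant drop-out in earlier groups, which was about 10 to 11%.

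On the ECog, the Assessment Methodology paragraph says: "Collateral informants (e.g., spouse, adult child, relative), when available, will complete questionnaires at weeks 0, 4, 8, and 21". Table 5 lists the ECog as a collateral measure and a secondary outcome. The inclusion criteria in Sections 9 and 10 do not ask for an informant; an informant is only one of four possible sources of the cognitive concern needed for MCI. Involvement of significant others is listed as a baseline characteristic and as a possible moderator.

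**The concern.** The plan accepts that some participants may have no informant, but its only power figure covering the ECog deducts nothing for them. This differs from a missed visit. A participant can attend every assessment and still have no ECog at any time point. The mixed model uses partial follow-up without imputation, but it recovers nothing for someone with no ECog at all. The H1 analysis rule, which H2 follows, needs a baseline and at least one post-baseline evaluation, so such a participant would not enter the ECog analysis.

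What is at stake is how the ECog result is read. It is the only collateral measure among the outcomes, and a null finding could be reported as coming from a comparison with 87% power when the true figure was lower.

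**Working it through.** **Inputs from the documents.** Two-sided alpha .02, 0.5 SD at the last time point, final sample 180 (90 per arm, 1:1), stated H2 power 87%. Alpha and sample size are stated for H1 and carried to H2. Informant availability *f* is not given and is an assumption here, varied from 50% to 100%.

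**Step 1: reproduce the 87%.**
- Slope test over four assessments with exchangeable correlation 0.5 (one of the listed values) and 86.4 per arm (216 × 0.8 = 172.8). With time scaled to 0–1 and equal spacing, Σ(t − mean)² = 5/9 = 0.556. The variance of the slope difference is 2 × 0.5 / (0.556 × 86.4) = 0.0208, so the standard error is 0.144. The noncentrality is 0.5/0.144 = 3.46, and power = Φ(3.46 − 2.326) = 87.2%. The actual weeks 0, 4, 8 and 21 give 87.8%.
- Plain two-sample comparison with 90 per arm: Φ(0.5 × √45 − 2.326) = Φ(1.028) = 84.8%, close to the 85% stated for H1.
- Slope test with the stated autoregressive correlation of .45 and 90 per arm: 57% (equal spacing) to 63% (actual weeks). This does not reproduce 87%.

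So 87% can be reached, but the calculation that reaches it has the whole post-drop-out sample contributing data.

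**Step 2: apply availability.** Calibrate to the plan's own figure. The noncentrality for 87% at alpha .02 is 2.326 + 1.126 = 3.453. With a fraction *f* of the 180 contributing ECog data, power = Φ(3.453 × √f − 2.326). For *f* = 0.80: 3.453 × 0.894 = 3.088, and Φ(0.762) = 77.7%. The two-sample formula with 90*f* per arm serves as a check.

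| Availability | N with ECog | Calibrated to 87% | Two-sample check |
|---|---|---|---|
| 100% | 180 | 87.0% | 84.8% |
| 95% | 171 | 85.1% | 82.7% |
| 90% | 162 | 82.9% | 80.4% |
| 85% | 153 | 80.4% | 77.8% |
| 80% | 144 | 77.7% | 75.0% |
| 70% | 126 | 71.3% | 68.4% |
| 60% | 108 | 63.6% | 60.7% |
| 50% | 90 | 54.6% | 51.8% |

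**Step 3: find where power crosses 80%.** Calibrated: f = ((2.326 + 0.842)/3.453)² = 0.842, or about 152 participants. The two-sample check crosses at about 89%, but it starts 2.2 points below 87% for reasons unrelated to informants, so the calibrated figure isolates the informant effect better.

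**Step 4: let drop-out be 10%.** Retained: 216 × 0.9 = 194.4. The crossing becomes 151.5/194.4 = 78% availability. At 90% availability, 175 participants have an ECog and power is Φ(3.453 × √(175/180) − 2.326), about 86%. Availability of 180/194.4, about 93%, would still give 180 participants with an ECog.

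**The case against.** **The text does not say that 87% applies to each measure.** H2 gives the figure for the hypothesis, whereas H3 gives its figure for each dependent measure. The use of 180 for H2 is also inferred from the reference back to H1. Both observations are correct. But if the 87% is not meant for the ECog, a named secondary outcome has no power statement, and the remedy is the same.

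**The 20% drop-out is conservative.** This has force. Against about 10% seen in the pilot groups, there is slack that could absorb a modest informant shortfall, as Step 4 shows. The plan does not make this argument, and the slack runs out at about 78% availability.

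**A larger true effect would compensate.** It would: 0.8 SD at 50% availability gives 93%. But the stated figure is for a medium effect, and the large effects cited under H2 concern subjective complaints rather than the ECog.

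**Stronger readings that the documents do not support.** A reader might infer that the ECog sample is below 180 by design, or that 87% holds only if every participant has an informant. Neither follows: 180 is a planning number after an allowance of up to 20%, and the plan permits an informant shortfall without establishing its size.

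A reader might also suspect that informants recruited after allocation would make the ECog subset differ between arms. The plan schedules informant questionnaires at week 0 and places baseline measures before randomisation. The H1 rule already requires a baseline and a post-baseline evaluation, so this is not a fault in the plan and no new analysis-set rule is needed.

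**Conclusion.** The point holds as a missing allowance in a stated figure. The 87% cannot be taken as the ECog's power, because nothing in the calculation covers retained participants without an informant. The direction is clear from the documents; the size is not, because no availability rate is given. On the assumptions above, the loss is about 2 points at 95% availability, 4 at 90%, 9 at 80% and 16 at 70%. Whether the 80% minimum is missed depends on both availability and drop-out: the threshold is about 84% availability with 180 retained and about 78% with 10% drop-out.

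The Neuro-QOL composite is self-reported and is not affected by informant availability. That should not be taken as confirmation of 87% for it: the figure was reproduced under an exchangeable correlation of 0.5 but not under the stated autoregressive .45, which gives 57 to 63%. That question, and the gap between 172.8 and 180, are separate from this point.

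This is a secondary outcome, and neither the sample size nor the primary inference changes. The correction is worth making because it is cheap and affects how a null ECog result would be interpreted.

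**What to change.** In the H2 power text, stop applying the 87% to the ECog. State the expected share of participants with an informant and its basis, for example experience at the two sites. Report a separate ECog power on the resulting number, with a short range such as 60 to 90% availability. If the sponsor wants to rely on drop-out below 20% to offset missing informants, the text should say so and show the resulting ECog sample.

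The cost is a few sentences and a less favourable stated figure for one secondary outcome. No extra data, participants or procedures are needed.
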